10.1 Summary Tables for Taste Assessments

Taste assessment data for questions 1 and 2 will be summarized using descriptive statistics (i.e. n, mean, SD, minimum, Q1, median, Q3, and maximum), for overall acceptability and each taste aspect by regimen.

For each of the questions, a breakdown of the number and percentages of subjects within each rating category will also be presented by regimen (within the same table as continuous summary statistics if appropriate).

10.2 Listings for Taste Assessment

All taste assessment data collected (i.e. categories for each question) will be listed for all enrolled subjects.

11 Safety Assessments

Safety data summaries will be presented by actual regimen and the safety analysis will be used throughout. All listing will be presented by all enrolled subjects.

11.1 Extent of Exposure and Treatment Compliance

The number and percentage of subjects dosed with IMP for each regimen will be summarised.

Dosing details (including the date and time of all IMP administrations and any comments) will be listed. Any recorded deviations from the planned dosing regimen will be listed as protocol deviations.

11.2 Meal Details

Meal details for fed dosing periods as recorded on the electronic case report form (eCRF) study build specification will be listed. Any recorded deviations from the planned meal times will be listed as protocol deviations.

11.3 Adverse Events

Throughout the study, all adverse events (AE) will be evaluated by the PI and noted in the AE section of the eCRF study build specification. An AE is any untoward medical occurrence in a subject that occurs either before dosing (referred to as a pre-dose AE) or once a medicinal product has been administered, including occurrences which are not necessarily caused by or related to that product.

AEs will be coded using the Medical Dictionary for Regulatory Activities (MedDRA v27.0), and reported by system organ class (SOC) and preferred term (PT) PT.

AEs will be classified into the following categories:

- Pre-dose AEs: AEs recorded at screening or with a start date and time prior to the first dose of IMP
- Treatment-emergent adverse events (TEAEs): AEs that commence during/after the first dose of IMP or commence before first dose of IMP (i.e. a pre-dose AE or existing medical condition) but worsen in intensity during exposure to IMP

TEAEs will be assigned to the regimen of the period in which the AE first occurred. Where the severity of an AE intensifies or symptoms change in a subsequent period, this will be defined as a new AE and included under the regimen associated with the subsequent period. AEs that occur during the washout period will be assigned to the regimen the subject received during the period immediately before the washout period.

Adverse events will be classified as “mild,” “moderate,” or “severe” when considering their severity.

Adverse events will be classified as “unrelated”, “possibly related,” and “related” when considering their relationship to IMP. TEAEs classified as “possibly related” and “related” will be defined as IMP-related events. An adverse drug reaction (ADR) is any AE where a causal relationship with the IMP is at least reasonable possibility, i.e., “possibly related” and “related”. Pre-dose AEs will always have the classification of “unrelated”.

If the severity or relationship to IMP of a TEAE is missing, the severity/relationship will be tabulated as “missing” in the summary tables.

When summary presentation is made by maximum severity, “missing” will be handled as follows:

- If there are other events (i.e., same SOC and PT code) with a maximum severity recorded as “moderate” or “severe” for that subject and regimen, then the maximum observed severity for that subject will be categorised and presented as “moderate” or “severe”, respectively
- If there are other events (i.e., same SOC and PT code) with a maximum severity recorded as “mild” for that subject and regimen, then the maximum observed severity for that subject will be categorised and presented as “missing”

When summaries are presented by relationship to regimen, “missing” will be handled as follows:

- If there are other events (i.e., same SOC and PT code) with a most closely related association recorded as “possibly related” or “related” for that subject and regimen, then the maximum observed relationship for that subject will be categorised and presented as “possibly related” or “related”, respectively.
- If there are other events (i.e., same SOC and PT code) with a most closely related association recorded as “unrelated” for that subject and regimen, then the maximum observed relationship for that subject will be categorised and presented as “missing”.

Where the start date of an AE is missing and the stop date is on or after the day of first administration of test-product, or both the start and stop dates are missing, then a “worst-case” scenario will be assumed i.e., the AE is assumed to have occurred post-administration and is therefore considered treatment-emergent. If a partial start date/time is available, then the event will be considered as treatment-emergent, unless the partial information suggests otherwise.

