11.3.1 Summary Tables for Adverse Events

All pre-dose AEs (as defined in [Section 11.3](#)) will be excluded from the summary tables, but will be listed.

Descriptive statistical methods will be used to summarise the TEAE data.

The number and percentage of subjects reporting each TEAE will be presented for both SOC and PT. For summaries by SOC and PT, with the exception of TEAEs by severity and relationship to IMP, the number of subjects, and the number of events will be summarised. For summaries by severity and relationship, only the number of subjects will be summarised.

For counts of subjects experiencing events the following will apply:

- A subject experiencing TEAEs in more than one body system, within a study period, will be counted once in the total number of subjects with TEAEs in that study period
- A subject with more than 1 TEAE in the same SOC, within a study period, counts only once at the SOC level
- A subject with more than 1 TEAE in the same PT, within a study period, counts only once at the PT level

For TEAE event counts, all events are included.

When it is necessary to calculate percentages, the denominator will be the total number of subjects in the safety analysis set for that regimen or study period and the numerator will be the total number of subjects reporting a TEAE within the relevant category.

Summaries presented for SOC and PT will be presented in descending order of frequency overall i.e. most frequently reported SOC in the study and then by most frequently reported PT in the study within each SOC.

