11.3.1.2 Summary of Treatment-Emergent Adverse Events

All subjects reporting TEAEs will be summarised by regimen and overall. Counts will be given for number of subjects and number of events. Subjects experiencing more than 1 TEAE within a regimen/overall will be counted only once for number of subjects but will be counted more than once for number of events.

Additionally, subjects reporting TEAEs will be summarised for SOC and PT by regimen and overall. Counts will be given for number of subjects and number of events.

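### SAP 11.3 places an AE that starts before the first dose and worsens after it in both the pre-dose and the treatment-emergent class, and no rule says which class prevails

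*SAP*

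**What the plan says.** SAP 11.3 sorts adverse events into two classes. The first is "Pre-dose AEs: AEs recorded at screening or with a start date and time prior to the first dose of IMP". The second, TEAEs, takes in events that start during or after the first dose and also events that "commence before first dose of IMP (i.e. a pre-dose AE or existing medical condition) but worsen in intensity during exposure to IMP".

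Further rules act on these classes:

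- **Causality (11.3).** "Pre-dose AEs will always have the classification of" unrelated.
- **Tables (11.3.1).** All pre-dose AEs, with a reference back to the definition in 11.3, "will be excluded from the summary tables, but will be listed".
- **Event counts (11.3.1).** "For TEAE event counts, all events are included".
- **Subject counts (11.3.1.2).** "All subjects reporting TEAEs will be summarised by regimen and overall".
- **Regimen (11.3).** "TEAEs will be assigned to the regimen of the period in which the AE first occurred".
- **Later worsening (11.3).** "Where the severity of an AE intensifies or symptoms change in a subsequent period, this will be defined as a new AE", reported under the regimen of that later period.

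**The concern.** The pre-dose definition has no exception for worsening, and the TEAE definition itself calls the worsened event a pre-dose AE. The same event can therefore be excluded from the tables under one sentence and counted under another. Two competent programmers could produce different TEAE and ADR tables from this text, each with a sentence to cite.

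These tables serve the secondary safety and tolerability objective. A pre-existing complaint that gets worse after dosing is the kind of event the second part of the TEAE definition exists to capture. The automatic causality rule also sits badly with Protocol 14.2 and 14.3, where the Investigator assesses the relationship of each AE and gives a final opinion at the end of the study.

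**Working it through.** The plan states no figure on this point, so the check is mainly logical: follow one event through every rule that could apply.

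**Test case.** A mild AE starts on Day -1 of Period 1 and becomes moderate after the Period 1 dose.

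1. *Pre-dose definition (SAP 11.3).* Onset is before the first dose, so the definition is met. The event is unrelated, is left out of the tables and appears in Listing 16.2.7.1.
2. *TEAE definition (SAP 11.3).* The event began before the first dose and worsened under drug, so this definition is also met. It enters the subject and event counts with its assessed relationship.
3. Results 1 and 2 cannot both be carried out. The remaining question is whether any other rule decides between them.

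**Possible tie-breakers.**

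- *New-AE rule (SAP 11.3).* If the worsening were recorded as a new AE with post-dose onset, the conflict would vanish. The rule is written only for worsening in a subsequent period. The mock listings place Day -1 within Period 1, so worsening from Day -1 to Day 1 stays inside one period. For an event with onset at screening, before any period, Period 1 could be read as a subsequent period and the rule might apply.
- *Missing-date rules (SAP 11.3 and 14.1).* These resolve a missing or incomplete start date towards treatment emergence. They do not cover a known pre-dose onset with later worsening. An AE with no start or stop date is therefore counted, while one documented as worsening after dosing may not be.
- *Listing shells (SAP 23).* The programming note to Listing 16.2.7.2 takes every TEAE date to be on or after the dose date, which leaves no place for a TEAE with pre-dose onset. The footnote to Listing 16.2.7.1 allows for pre-dose AEs that end after dosing. Both suggest sorting by onset date.
- *Protocol.* Section 14.1 describes a pre-dose AE as one occurring before dosing and says nothing about worsening. The protocol supplied does not define TEAE.

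No rule clearly settles the case.

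**Regimen.** With onset on Day -1, the first-occurrence rule can be read as giving the Period 1 regimen. With onset at screening there is no period to point to, so the attribution gap is clear only there.

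**Size.** SAP 11.3.1 uses the safety analysis set for the regimen as denominator. If k subjects are dropped who have no other event in the same table row, incidence falls by 100 × k / N percentage points.

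- N = 16 (planned, SAP 5.3), k = 1: 100 × 1/16 = 6.25 points.
- N = 12, k = 1: 100 × 1/12 = 8.3 points. Twelve is the minimum number of evaluable subjects in SAP 5.3, used here only as a lower illustration of N.

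The documents give no value for k.

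**The case against.** The strongest reply is that the SAP already answers the question. The second part of the TEAE definition is its only text on an event that starts before dosing and then worsens, and it calls that event a TEAE. Read with the specific provision over the general one, it removes the event from the pre-dose class, and the counting rules in 11.3.1 and 11.3.1.2 then include it. This reading is reasonable and may well be what was intended. It is not stated, however, and the exclusion in 11.3.1 covers all pre-dose AEs as defined, without exception.

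The practical reach is also limited, and these points stand:

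- Several exclusion criteria, including recent diarrhoea, a cold, abnormal laboratory results and general fitness, are re-assessed at admission or pre-dose in Period 1 (Protocol 9.3). This should reduce the number of AEs present at first dose.
- Pre-dose AEs remain listed with severity and relationship.
- The stopping criteria in Protocol 8.5 use the Investigator's view of relatedness, not the SAP tables.
- With 8 subjects per sequence, any loss in Period 1 does not favour tablet or suspension by design.

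A reader might infer that worsening under drug can never be recorded as related. The documents do not support that: the Investigator still assesses every AE under the protocol. What is at risk is how the event is classified in the SAP tables. A reader might also set one lost case against the 8.7% headache rate in Protocol 5.3.2. That rate covers all headache TEAEs over single and multiple doses of 50 to 1600 mg. It is not a rate of pre-dose onset followed by worsening, so the comparison is not like for like.

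**Conclusion.** The SAP contradicts itself on AEs that start before the first dose and worsen after it, and it gives no precedence rule. The contradiction follows from the wording alone and needs no assumption about data.

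It is tempting to conclude that the plan definitely leaves these events out. The documents do not support that, because they also direct that such events be treated as TEAEs and counted. An undercount arises only if the exclusion is applied literally. In that case TEAE and ADR counts can only fall, by 6.25 points per affected subject in a column of 16. This assumes the subject has no other event in the same row. The frequency is unknown and probably low. The consequence is confined to the safety tables of a secondary objective, but the text should be corrected before those tables are programmed.

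**What to change.** Make the two classes mutually exclusive in SAP 11.3 and 11.3.1:

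1. Define pre-dose AEs as those that start before the first dose of IMP and do not worsen in intensity after it. Use the same phrase for worsening in the TEAE definition, so that no event falls between the two.
2. Limit the table exclusion and the automatic unrelated classification to that redefined class.
3. Treat an AE that worsens after the first dose as a TEAE, or record the worsening as a new AE with onset at the time of worsening. Either way, assign it to the regimen on which it worsened and keep the Investigator's causality rating. Assigning every such event to the Period 1 regimen would be wrong where worsening first occurs in a later period. It would also be wrong for replacement subjects, who may begin with a later regimen (Protocol 8.4).
4. Align the notes to Listings 16.2.7.1 and 16.2.7.2 with the option chosen.

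The cost is a few lines of SAP wording and one derivation flag. Protocol 15.4 requires the analysis plan to be signed off before database lock, so the change belongs before that point. The one practical condition is that the eCRF captures the time of worsening, which the documents do not confirm.

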8.1 Study Plan

This is a Phase 1, single centre, single part, partially randomised, open-label, relative bioavailability study in healthy subjects.

It is planned to enrol approximately 16 healthy male and healthy non-pregnant, non-lactating female subjects.

An evaluable subject for the relative bioavailability assessment will have received delafloxacin Powder for Oral Suspension (test) and the oral delafloxacin Tablet

(reference) at the same dose level, in the fasted state, and have evaluable PK and safety data to 48 hours post-dose.

An evaluable subject for the food effect assessment will have received delafloxacin Powder for Oral Suspension in the fed and fasted state, at the same dose level, and have evaluable PK and safety data to 48 hours post-dose.

It is planned to administer up to four regimens ([Table 2](#)).

Table 2 Description of Regimens

Period	Regimen	Investigational Medicinal Product	Dose	Route of Administration
1 and 2	A	delafloxacin Tablet (reference)	450 mg	Oral, Fasted
	B	delafloxacin Powder for Oral Suspension, reconstituted with orange flavoured vehicle	450 mg	Oral, Fasted
3	C	delafloxacin Powder for Oral Suspension, reconstituted with orange flavoured vehicle	450 mg or XX mg	Oral, Fed or Oral, Fasted
4 (optional)	D	delafloxacin Powder for Oral Suspension, reconstituted with orange flavoured vehicle	XX mg or YY mg	Oral, Fed or Oral, Fasted

Details of the IMPs are provided in [Section 5.2](#). The order in which regimens are dosed may be subject to change due to logistical reasons

The effect of food on the PK of a novel delafloxacin Powder for Oral Suspension formulation may be explored in Period 3 or optional Period 4, by administering IMP after a high-fat breakfast. The effect of increasing or decreasing the dose level may also be explored.

There will be an interim decision meeting after Periods 2 and 3 to review the PK and safety data for up to 48 hours post-dose from preceding periods, in order to determine the dose and prandial state for Regimen C and Regimen D (if applicable).

There will be a minimum washout of 4 days between dosing in Periods 1 and 2. The intervals between Periods 2 and 3, and Period 3 and optional Period 4, will require a minimum of 14 days, to permit the interim decision process and IMP manufacture.

The study will follow the design in [Figure 1](#).

Subjects will undergo preliminary screening procedures for the study at the screening visit (Day -28 to Day -2).

Periods 1 and 2

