10.3.5 Follow-up

A follow-up phone call will take place on Day 6 ± 1 of the final treatment period, to ensure the ongoing wellbeing of the subjects. If a subject reports any AEs that present a cause for concern, they will be required to attend the clinical unit for an (unscheduled) follow-up visit; assessments may be performed at the unscheduled follow-up visit, as detailed in the schedule of assessments. Completion of the last follow-up phone call or unscheduled follow-up visit will be considered the end of the study.

11 Dosing of Subjects

Dosing will be performed at the time points detailed in the study schedule of assessments in [Appendix 2](#).

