14.1 Definition and Classification of Adverse Events

An AE is any untoward medical occurrence in a subject that occurs either before dosing (referred to as a pre-dose AE) or once a medicinal product has been administered, including occurrences which are not necessarily caused by or related to that product.

An ADR is any AE where a causal relationship with the IMP is at least a reasonable possibility (possibly related or related).

AEs will be monitored from the time that the subject signs the ICF until after the follow-up phone call/unscheduled follow-up visit. The severity of AEs should be assessed as follows:

- Mild** An AE that is easily tolerated by the subject, causes minimal discomfort and does not interfere with everyday activities.
- Moderate** An AE that is sufficiently discomforting to interfere with normal everyday activities; intervention may be needed.
- Severe** An AE that prevents normal everyday activities; treatment or other intervention usually needed.

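### For comparisons involving Regimen C or D, assigning washout adverse events to the preceding regimen sets TEAE percentages side by side that rest on unequal observation time; A versus B is balanced

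*SAP*

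**What the plan says.** SAP 11.3 counts as treatment-emergent "AEs that commence during/after the first dose of IMP", together with pre-dose events that worsen. It gives no end of the risk period. On allocation to regimen it says "AEs that occur during the washout period will be assigned to the regimen the subject received during the period immediately before the washout period". For percentages, SAP 11.3.1 says "the denominator will be the total number of subjects in the safety analysis set for that regimen or study period", so subjects are the denominator, not time. Mock Tables 14.3.1 to 14.3.6 place the regimens in adjacent columns.

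Collection is continuous. Protocol 14.1: "AEs will be monitored from the time that the subject signs the ICF until after the follow-up phone call/unscheduled follow-up visit".

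Three statements fix how long each regimen collects events:
- Protocol 8.1: "There will be a minimum washout of 4 days between dosing in Periods 1 and 2".
- Protocol 8.1: "The intervals between Periods 2 and 3, and Period 3 and optional Period 4, will require a minimum of 14 days".
- Protocol 10.3.5: "A follow-up phone call will take place on Day 6 ± 1 of the final treatment period".

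Protocol 8.8 randomises 8 subjects to AB and 8 to BA. Periods 3 and 4 are not randomised: C is given only in Period 3 and D only in optional Period 4.

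**The concern.** Under the attribution rule, each regimen owns every event from its dose until the next dose or the final call. That span is set by logistics: a short residential washout, a long gap for the interim decision and manufacture, or a brief follow-up after the last dose. It has nothing to do with formulation, dose or food. A regimen followed by a long gap collects more unrelated complaints than one followed by a call a few days later.

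Regimens C and D exist to examine food state and dose level, and Protocol 5.3.2 reports that earlier data suggest more frequent and more severe diarrhoea at higher doses. Readers will therefore compare these columns with B, or with each other. Safety and tolerability is a secondary objective, and these tables are its main summary. At stake is a tolerability statement about a fed or changed-dose regimen that partly reflects the calendar.

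**Working it through.** The documents give no adverse event rate or observation time per regimen, so there is no stated figure to reproduce. The check is subject-day arithmetic.

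**Inputs.** Period 1 to 2: 4 days. Period 2 to 3 and Period 3 to 4: 14 days each. All three are minimums (Protocol 8.1). Final dose to call: Day 6 minus Day 1 = 5 days, range 4 to 6 (Protocol 10.3.5). Sequences: 8 AB, 8 BA (Protocol 8.8).

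**Formula.** Days for a regimen = sum over subjects of the time from that dose to the next dose, or to the call.

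| Regimen | Subject-days | Mean per subject |
|---|---|---|
| A | 8×4 + 8×14 = 144 | 9 |
| B | 8×14 + 8×4 = 144 | 9 |
| C, Period 4 follows | 16×14 = 224 | 14 |
| C, last regimen | 16×5 = 80 | 5 (4 to 6) |
| D | 16×5 = 80 | 5 (4 to 6) |

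**Ratios.** A:B = 1.00. C:B = 14/9 = 1.56 with Period 4, or 5/9 = 0.56 without, so the direction depends on whether Period 4 is run. D:B = 0.56. C:D = 14/5 = 2.8.

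**Illustrative effect.** Assume a constant background rate λ of unrelated events, equal in all regimens. The documents give no λ; I used 0.005 to 0.03 per subject-day. Expected events = λ × subject-days. The percentage with at least one event is the mean over subjects of 1 − exp(−λt).

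| | λ = 0.005 | λ = 0.01 | λ = 0.03 |
|---|---|---|---|
| A, B | 4.4% | 8.5% | 22.8% |
| C, Period 4 follows | 6.8% | 13.1% | 34.3% |
| C last, or D | 2.5% | 4.9% | 13.9% |

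At λ = 0.01 the expected counts are 1.44 (A and B), 2.24 (C followed by Period 4) and 0.80 (C last, or D). The gaps are 2.24 − 0.80 = 1.44 events for C against D, and 1.44 − 0.80 = 0.64 for B against D or against a final C.

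**Sensitivity.**
- Protocol 8.1 does not say whether the 14 days run dose to dose. Discharge to admission would give about 16 days: A and B 10, C 16, D 5.
- The minimums plus 28 days of screening sum to 28 + 4 + 14 + 14 + 5 = 65 days, against about 14 weeks (98 days) in the synopsis. If all the excess fell in the two later gaps (an assumption), each would be (98 − 28 − 4 − 5)/2 = 30.5 days. Means would be 17.25 for A and B, 30.5 for C and 5 for D.
- A versus B stays equal only while the sequences do. With 8 AB and 4 BA, A has (8×4 + 4×14)/12 = 7.3 days and B (8×14 + 4×4)/12 = 10.7.

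**Common 72 h window.** Each regimen has 16×3 = 48 subject-days. At λ = 0.01 every column has the same background percentage, 1 − exp(−0.03) = 3.0%.

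**The case against.** The case for leaving the plan alone has weight.

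- The TEAE summaries are descriptive, and the objective is to add safety information, not to rank regimens. C and D are non-randomised, so B against C or D is confounded with period whatever window is used. This stands, and a common window removes only the unequal-time part.
- Unrelated events are already separable. Protocol 14.2 bases causality partly on timing, Tables 14.3.4 and 14.3.5 show relationship and ADRs, and Listing 16.2.7.2 gives dose and onset times. This also stands, but the overall and SOC/PT TEAE tables still pool early and late events.
- In earlier oral Phase 1 studies most of the commonest events were treatment-related (diarrhoea 12.3 of 13.5%, nausea 4.2 of 5.2%; Protocol 5.3.2). Capture at home may also be lower than in the unit. Both would shrink the effect, and the constant λ above ignores the second.
- A short cut-off could hide late drug effects, since five half-lives describes elimination, not risk. This argues against removing late events from regimen columns; it does not argue against showing them separately.

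A reader might infer more than the documents support. One inference is that every by-regimen comparison is biased, including tablet against suspension at 450 mg fasted. It is not: the 4-day and 14-day gaps cancel under 8 AB and 8 BA. Another is that the long gaps distort the dose and food decisions. Protocol 8.1 describes those reviews as using safety data up to 48 hours post-dose, which every regimen has.

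**Conclusion.** The point holds for comparisons involving C or D. Mean observation time at the minimum intervals is 9 days for B, against 14 or 5 for C and 5 for D, and the SAP plans neither a common window nor a time-adjusted summary. The regimen with the longer gap will tend to show the higher TEAE percentage without any treatment difference. The 2.8-fold ratio arises only if optional Period 4 is run; otherwise the contrast is 9 against 5 days.

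The expected distortion in 16 subjects is small, about 0.6 to 1.4 events at the assumed 0.01 per day. It scales with a background rate that the documents do not give, and it grows if the real gaps exceed the minimum. This is a low-cost improvement to presentation. It does not touch the PK objectives or the randomised comparison.

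**What to change.** Keep the attribution rule in SAP 11.3 and all planned tables. In SAP 11.3.1:

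1. Split the overall by-regimen summary and the SOC/PT summary (Tables 14.3.1 and 14.3.2) by onset: within 72 h of dosing, and later. Protocol 9.4 takes five half-lives as 3 days, and Protocol 11.2 makes five half-lives the floor for any shortened washout. 72 h also falls before the earliest call on Day 5. A 96 h cut-off would not be safe on either count.
2. Apply the same split to the TEAE, ADR and serious rows, so that no subset can exceed its total.
3. Footnote the observation days per regimen, from dose to next dose or last contact. Note that a subject with both early and late events appears in both parts, so event counts add up but subject counts need not.
4. Say how an event with an incomplete onset time is placed, for example in the early part unless the partial information excludes it, in line with the SAP's existing worst-case rule.
5. Base between-regimen tolerability statements involving C or D on the 72 h columns.

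The cost is one derived flag and slightly longer tables. No new data are needed, and no event leaves its regimen column. Protocol 15.4 has the analysis plan signed off before database lock, so the split should be specified by then.
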